A survey of international practice in terms of surgical margins and dose has been carried out and indicated that approximately 60% of clinicians applied a 5cm margin to the surgical scar when planning post-operative radiotherapy and the same margin to the tumour bed when planning pre-operative treatment (Robinson 1998 personal communication). Lindberg and Suit have previously recommended larger margins (7-15cm) depending on size and grade of tumour. There are very few studies in the literature looking at the target volume used when planning radiotherapy and this tends to be poorly reported. One group found a remarkable difference in 5-year local control where the margin was <5cm (30%) or >=5cm (93%) (Mundt 1995). This conflicts with the brachytherapy data where acceptable results are achieved using 4cm margins longitudinally and 2cm laterally. (Fein *et al*; 1995). This author also reported that local control was dose dependent. Fein 1995 noted that patients receiving <62.5Gy had 5-year local control of 78% v 95% where the dose was >62.5Gy. (Robinson *et al*; 1992) failed to demonstrate a variation in local control according to dose, although the response rate to pre-operative radiotherapy was clearly dose dependent.

It is common practice for clinicians to use a 'shrinking field' technique for the treatment of extremity sarcomas. A typical phase 1 dose is 50Gy in 25 daily fractions followed by a 10-16Gy boost in 5-8 fractions. A recent publication from the Royal Marsden Hospital has suggested that as in other tumour sites the great majority of local recurrences occur within the high dose volume (Cleator, 2001). This rises the question regarding the large volume phase 1 being necessary or if the boost is necessary where an adequate surgical margin has been achieved.

There is currently an influx of new radiotherapy techniques such as Intensity-Modulated Radiotherapy (IMRT) being introduced, which will permit the selective sparing of normal tissues. There is a need to accurately determine the volumes that can safely be spared before implementing these techniques. Prior to considering the implementation of IMRT techniques (Millar, 2001) it is important to obtain relevant and accurate dose/volume data, which can be collated with functional outcomes.

Rationale

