6. STATISTICAL CONSIDERATIONS

Analysis of outcome measures

The primary research hypothesis for the trial is that a reduced volume of post-operative radiotherapy treatment for adult extremity soft tissue sarcomas will improve limb function without compromising local control. Secondary research hypotheses are that the reduced treatment improves toxicity, overall level of disability and is not inferior to the standard treatment in terms of disease-free survival and overall survival.

The primary analysis for the trial is to compare the experimental treatment to the control treatment in terms of benefit to limb function and non-inferiority for time to local recurrence. For limb function, TESS will be analysed using longitudinal statistical methods, in particular summary measures analysis. The two treatment groups will be compared in terms of TESS at 2 years and area under the curve using either t-tests or Wilcoxon tests depending on the distribution of the data. The proportion of patients in each treatment arm who report small, medium or large change (with worsening or improvement reported separately) between each assessment interval will be required. For time to local relapse, statistical analysis will be based on a one-sided 95% confidence interval for the hazard ratio and non-inferiority will be inferred when the entire confidence interval falls above the non-inferiority margin of 0.63 (equivalent to a difference of 80% versus 70% in 2-year local relapse-free rates).

The rates of grade 3 or 4 toxicity on the two treatment arms will be compared using chisquare tests. Overall level of disability will be analysed using longitudinal statistical methods similar to those used for TESS. Statistical analysis for disease-free survival and overall survival will be based on one-sided 95% confidence intervals for the hazard ratio to assess non-inferiority.

Interim analysis

Interim analyses will be carried out annually and presented to an independent Data Monitoring Committee (DMC). The interim analyses will present recruitment data and data on all primary and secondary outcomes.

Final analysis

The study is expected to complete recruitment within 4 years. Final analysis will be carried out after all patients have been followed up for a minimum of two years.

Calculation of sample size

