Sample size calculations are based on the two primary outcome measures of limb function and time to local recurrence. In relation to limb function, a difference in TESS score between the two treatment arms of 10 points would indicate a clinical benefit to patients (Davis, personal communication). Previous data has suggested an expected standard deviation for the score of 20. The key analysis for this outcome measure is the difference in score at two years. Assuming a null hypothesis of no difference will be tested using a t-test with 5% significance level and assuming a standard deviation of 20, 105 patients per treatment arm will be needed to detect this size of difference at two years with 95% power.

In relation to local relapse, sample size is calculated based on showing that the 2-year local relapse rate on the experimental treatment arm is non-inferior to that on the control arm. The two-year local relapse-free rate on the control treatment is expected to be 80% and a decrease in this rate to 70% would be the largest difference between treatments that can be judged as clinically acceptable. A non-inferiority margin of 70% is therefore chosen as relevant for this trial. With 198 patients per arm with full follow-up for two years and using a one-sided 95% confidence interval there will be 80% power to detect non-inferiority in two-year local relapse-free rates of 10% or less.

In conclusion, with 200 patients per treatment arm, there will be 95% power to detect a difference of 10 points in the TESS score between the treatment arms at two years and 80% power to determine non-inferiority in local relapse-free rates with non-inferiority defined as a difference in two-year local relapse-free rates of 10%.

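### The stated 80% power for local relapse belongs to a comparison of 2-year proportions, not to the hazard-ratio analysis the protocol plans; the power of that analysis is not given

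*Protocol*

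**What the plan says.** Section 6 of the protocol deals with local relapse in two places.

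Under Analysis of outcome measures the method is fixed: "For time to local relapse, statistical analysis will be based on a one-sided 95% confidence interval for the hazard ratio". Non-inferiority is declared if the whole interval lies above a "non-inferiority margin of 0.63 (equivalent to a difference of 80% versus 70% in 2-year local relapse-free rates". A value below 1 as the unfavourable limit means that the ratio is control over experimental.

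Under Calculation of sample size the trial is sized on relapse-free proportions at 2 years. The control rate is an expectation given without a source ("The two-year local relapse-free rate on the control treatment is expected to be 80" per cent), the largest acceptable fall is to 70%, and the result is "With 198 patients per arm with full follow-up for two years and using a one-sided 95% confidence interval there will be 80% power". The closing paragraph of that subsection repeats the 80% for 200 patients per arm. Neither paragraph gives a number of relapses or a power for the hazard-ratio test.

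Three other statements bear on the point. Section 2 censors time to local recurrence at last follow-up, not at 2 years. Section 6 places the final analysis after every patient has at least 2 years of follow-up. Sections 3 and 8 plan recruitment from March 2006 to March 2010 and analysis in March 2012.

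**The concern.** The sizing and the analysis use different tests. A test of proportions with complete follow-up gets its power from the number of patients; a hazard-ratio test gets it from the number of events. The 80% cannot be carried from one to the other without an event calculation, and none is given.

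Local relapse is the co-primary outcome that guards against under-treatment with the smaller volume. Investigators, the monitoring committee and later readers will take 80% as the chance of showing non-inferiority when the arms are truly equal. If the real chance is lower, an inconclusive result becomes more likely simply because there are too few relapses, and the protocol gives the reader no means of seeing this.

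**Working it through.** **Inputs from the protocol (section 6 unless noted).** One-sided alpha 5% (z = 1.645); power 80% (z = 0.842); 2-year relapse-free rate 80% on control; 10-point margin; hazard-ratio margin 0.63; 198 per arm in the calculation and 200 per arm planned; 4 years of accrual and at least 2 years of follow-up; censoring at last follow-up (section 2). **Assumed, because not stated:** truly equal arms and uniform accrual.

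**1. The protocol's own figure.** Difference of two proportions, unpooled variance:

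n per arm = (1.645 + 0.842)² × (0.8×0.2 + 0.8×0.2) / 0.10² = 197.8, so 198.

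Power is 80.0% at 198 and 80.4% at 200 per arm. Other readings do not give 198: one-sided 2.5% gives 252, and a one-sided pooled test of 80% against 70% gives 231 (251 with continuity correction). The arithmetic is right, and the test it belongs to is identified.

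**2. The margin.** ln 0.8 / ln 0.7 = 0.6256, rounded in the protocol to 0.63.

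**3. Events needed for the hazard-ratio test.** Schoenfeld: d = 4(1.645 + 0.842)² / (ln 0.63)² = 115.8, so 116; at the unrounded 0.6256, 112.4, so 113. Freedman gives 120 and 117.

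**4. Power on the protocol's 2-year inputs.** 400 × 0.20 = 80 relapses.

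Power(d) = Φ(0.462 × √d / 2 − 1.645)

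Power(80) = Φ(2.066 − 1.645) = Φ(0.421) = 66%.

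Across Schoenfeld and Freedman, margins 0.63 and 0.6256, and 396 or 400 patients, the range is 65% to 67%. A Cox simulation with 198 per arm and exactly 2 years of follow-up (10,000 runs) gives 66.2%.

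**5. The final analysis, with later relapses counted.** Follow-up then runs from 2 to 6 years. The early hazard is λ = −ln(0.8)/2 = 0.1116 per year. Let the hazard after year 2 be r × λ. Without dropout,

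events = 400 × {0.2 + 0.8 × [1 − (1 − e^(−4rλ)) / (4rλ)]}.

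For r = 0.5, 4rλ = 0.223, and the result is 400 × (0.2 + 0.8 × 0.1037) = 113. The right-hand columns add an assumed 5% per year censored by death or loss, a rate that is not in the protocol.

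| Hazard after year 2, relative to early | Events, no dropout | Power | Events, 5% a year censored | Power |
|---|---|---|---|---|
| 0 | 80 | 66% | 76 | 65% |
| one quarter | 97 | 74% | 91 | 71% |
| one half | 113 | 79% | 104.5 | 76% |
| equal | 142 | 87% | 129 | 84% |

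Simulation of the last row without dropout, with 198 per arm, gives 85%. Solving for 116 events gives a break-even r of about 0.55 without dropout and about 0.73 with 5% a year censored.

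**The case against.** The strongest reply is that the hazard-ratio analysis is not cut at 2 years. Follow-up at the final analysis is about 2 to 6 years, later relapses count, and with a constant hazard the planned test has more than the stated power. This stands. A reader might infer from the 66% that the trial lacks its stated power; the protocol does not support that, because 66% is the power of the final analysis only if no relapse occurs after year 2.

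It is also fair to say that the sample-size text refers to 2-year rates and that its figure is correctly computed. So this is a mismatch between sizing and analysis, not a calculation error. And event details may sit in a statistical analysis plan. But the power claim itself stands in the protocol, beside an analysis to which it does not apply.

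Three further inferences should be resisted:

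- **Much lower relapse rates.** The Introduction cites "5-year local control where the margin was <5cm (30%) or >=5cm (93"%) and "patients receiving <62.5Gy had 5-year local control of 78% v 95% where the dose was >62.5Gy". Applied to the control arm at a constant hazard without deaths, 93% to 95% at 5 years would mean about 16 to 23 events and 24% to 30% power. These are two single series. The Introduction itself notes that the first conflicts with brachytherapy results, and this trial admits microscopically positive margins. They support a sensitivity range, not a prediction.
- **Almost no allowance for loss.** The gap between 198 and 200 per arm matters for the test of proportions. In the hazard-ratio analysis, patients who die or are lost contribute until they are censored.
- **Weaker protection of patients.** Low power does not raise the 5% risk of falsely declaring non-inferiority. It raises the risk of an inconclusive trial.

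**Conclusion.** The concern holds in conditional form. The 80% is correct for a difference in 2-year proportions and is not the power of the planned hazard-ratio analysis. For that analysis, 80% needs about 113 to 120 relapses, against 80 expected by 2 years on the protocol's own rates (about 66% power). By the final analysis power lies between 66% and 87% without dropout, depending on a hazard after year 2 that the protocol does not state; censoring by death or loss lowers it. The 80% is therefore unsupported for the planned analysis rather than shown to be unattainable.

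These figures assume truly equal arms, uniform 4-year accrual, a constant hazard within each period and an 80% control rate at 2 years. The point should be fixed, but it does not threaten the validity of the non-inferiority test.

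**What to change.** In Calculation of sample size, change both the local-relapse paragraph and the closing paragraph:

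- State that the 80% applies to the difference in 2-year relapse-free proportions with complete 2-year follow-up.
- For the hazard-ratio analysis, give the number of relapses required for 80% power (about 113 to 120, depending on method and rounding of the margin).
- Give the number of relapses expected at the final analysis, with the assumed hazard after year 2 and the assumed rate of death or loss, and the resulting power.
- Add a short table of power by number of relapses at margin 0.63 and one-sided 5%, for example 40: 43%; 80: 66%; 116: 80%. The row of 40 corresponds to 10% relapsing by 2 years among 400 patients. Lower relapse rates should be shown as a sensitivity range only.

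The cost is wording, and possibly a less favourable stated power. The number of patients, the analysis method and its timing need not change.

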7. STRATIFICATION

Patients will be stratified by tumour grade, adequacy of surgical clearance and centre.

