3. STUDY DESIGN

Type of Design

This is a prospective phase III, multicentre, randomised controlled clinical trial.

Patients will be required to give informed consent twice: at registration and randomisation.

Patients will be registered into the trial prior to surgery, in order to have the initial assessments and to have the option to take part in the VORTEX-BIOBANK sub-study.

Patients will be randomised into the trial after surgery, once it has been confirmed that they are still eligible for radiotherapy treatment and the treatment options have been explained to them by a consultant oncologist/radiotherapist.

Patients must be randomised within a time frame so that trial treatment will commence within 12 weeks of surgery.

Trial Schema

Biopsy Assessment of extent of tumour by imaging

* Patient registration and completion of pre-operative TESS questionnaire

Wide local excision of sarcoma

Wound healing and assessment

Oncology appointment post-operation

*Randomisation

Stratified by: tumour grade, adequacy of definitive surgical clearance and centre

Radiotherapy planning

Control Arm Conventional two-phase treatment

Total dose: 66Gy in 33#							
Weeks 1-5: 2Gy x 5 days Weekly	CTV ₁ : 5cm margin to GTV or 1cm to the scar, whichever is longer in the cranio-caudal direction and minimum margin of 2cm axially						
Week 6 2Gy x 5 days	CTV ₂ 2 cm cranio- caudal margin to						
Week 7	GTV and minimum margin						

Research Arm Single-phase treatment to CTV₂ only Total dose: 66Gy in 33#

Weeks 1-6: 2Gy x 5 days Weekly	CTV ₂ 2 cm cranio- caudal margin to GTV and minimum margin of 2cm axially
Week 7 2Gy x 3 days	

minimum margin

of 2cm axially

CTV: Clinical Target Volume

2Gy x 3 days

^{*}Patient Registration and TESS completion after written informed consent obtained

^{**} Patient to be randomised in order for protocol treatment (radiotherapy) to begin within 12 weeks of surgery

Schedule of Events

VorteX	Pre-op	Surgery	Post-op Assessment Upon Discharge ◆	Post-op Oncology Appointment ••	RT treatment: weekly during Weeks 1-7	3 months post-op	6 months post-op	9 months post-op	12 months post-op	15 months post-op	18 months post-op	21 months post-op	24 months post-op	6 monthly Follow-up (24 months to 5 years)	Annual Follow-up (5 Years onwards)
WHO Performance Status	Χ	-	-	-	Χ	Χ	Х	X	Χ	X	X	X	Χ	X	X
Acute Skin Morbidity Assessment	-	-	-	-	X	ı	-	-	-	-	-	-	-	-	-
Wound Assessment	-	-	X	X	X	X	Х	-		-	-	-		-	-

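### Randomisation is stratified by grade, clearance and centre, but no analysis stated in section 6 uses these factors, and the 0.63 margin is not tied to a stratified or an unstratified hazard ratio

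*Protocol*

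**What the plan says.** The trial schema in section 3 applies the factors at randomisation: "Stratified by: tumour grade, adequacy of definitive surgical clearance and centre". Section 7 repeats the list: "Patients will be stratified by tumour grade, adequacy of surgical clearance and centre".

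Section 6 (Analysis of outcome measures) then names these methods:

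- **TESS at two years and area under the curve:** t-tests or Wilcoxon tests. The sample-size section repeats the t-test for the two-year score.
- **Grade 3 or 4 toxicity:** chi-square tests.
- **Local relapse:** "statistical analysis will be based on a one-sided 95% confidence interval for the hazard ratio". The limit is a "non-inferiority margin of 0.63 (equivalent to a difference of 80% versus 70% in 2-year local relapse-free rates".
- **Disease-free and overall survival:** one-sided 95% intervals for the hazard ratio.

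None of these statements mentions grade, clearance or centre. The TESS and toxicity tests are unadjusted as named. The hazard-ratio statements name no model.

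**The concern.** A trial that balances its arms on chosen factors normally analyses by them too. Stratified randomisation removes between-stratum variation from the comparison of arms. A plain two-sample test still counts that variation in its standard error, so some of the precision gained by the design is not used.

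For the hazard ratio the question is which quantity is being estimated. When the strata differ in relapse risk and treatment has an effect, the ratio within strata is further from 1 than the ratio over the whole arm. The protocol gives one numerical margin and does not say which ratio it applies to. Local relapse is a primary outcome decided by a single confidence bound, so two defensible analyses could fall on opposite sides of 0.63. It is better to fix the choice before outcome data are seen, and section 6 sends data on all outcomes to annual interim analyses.

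**Working it through.** **The plan's own figures reproduce.** Non-inferiority of proportions at 80% in both arms, a 10-point margin, one-sided 5% and 80% power gives 198 per arm, as stated. TESS with difference 10, SD 20, two-sided 5% and 95% power gives 105 per arm by the exact t-test. The margin is ln(0.80)/ln(0.70) = 0.2231/0.3567 = 0.626, stated as 0.63 (control over research). None of these depends on the stratification factors.

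**TESS.** Let the factors explain a share R² of the variance (assumed 10 to 20%; the protocol gives no figure). With arms balanced within strata, the true standard error is SD × √((1 − R²) × 2/n), while the t-test uses SD × √(2/n). Under no difference, the test rejects when a standard normal exceeds 1.96/√(1 − R²):

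- R² = 0.10: 1.96/0.949 = 2.066, two-sided error 3.9%.
- R² = 0.20: 1.96/0.894 = 2.191, two-sided error 2.8%.

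With SD 20 and 200 per arm all assessed, the 95% half-width is 1.96 × 20 × √(2/200) = 3.92 points unadjusted. It would be 3.92 × 0.949 = 3.72 or 3.92 × 0.894 = 3.51 adjusted.

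**Hazard ratio: whole-arm against within-stratum.** Assume 60% high grade, 25% inadequate clearance, independent factors with relapse hazard ratio 2 each, and exponential times. The stratum weights are 0.30 (neither), 0.55 (one) and 0.15 (both), with relative hazards 1, 2 and 4. Write a for the two-year cumulative hazard in the lowest-risk stratum. Then 0.30e^(−a) + 0.55e^(−2a) + 0.15e^(−4a) = 0.80 gives a = 0.1144.

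- A within-stratum ratio of 1/0.63 = 1.587 gives a research-arm two-year rate of 0.250 + 0.383 + 0.073 = 70.5%. With factor ratios of 3 it is 71.1%.
- A research-arm rate of exactly 70% needs a within-stratum ratio of 1.62 (factor ratio 2) or 1.66 (factor ratio 3). In the protocol's orientation these are 0.616 and 0.601.

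**Hazard ratio: error rates.** I simulated 400 patients, 1:1 within four strata, with two independent 50/50 factors each with relapse hazard ratio r, an 80% control rate at two years, the unrounded margin 0.626, and 6,000 trials per setting. Centre was not modelled. Section 6 says "Final analysis will be carried out after all patients have been followed up for a minimum of two years"; with four years of accrual, follow-up runs from 2 to 6 years. The Monte Carlo standard error is √(0.05 × 0.95/6000), about 0.3 points. Entries are the probability of declaring non-inferiority, unstratified / stratified.

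| True state | Follow-up | r = 1.5 | r = 2 | r = 3 |
|---|---|---|---|---|
| Within-stratum ratio at 0.626 | 2 years | 5.3 / 5.2% | 5.4 / 5.0% | 5.6 / 4.6% |
| Within-stratum ratio at 0.626 | 2 to 6 years | 5.1 / 4.6% | 6.3–6.6 / 4.8–5.3% | 8.2–8.7 / 5.1% |
| Whole-arm 80% v 70% | 2 years | 5.0 / 5.0% | 4.8 / 4.4% | 4.1 / 3.2% |
| Whole-arm 80% v 70% | 2 to 6 years | not run | 5.2 / 4.3% | 5.4 / 2.9% |

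**Power with truly equal arms, 2 to 6 years.** There is no shift in the estimate (unstratified ratios 0.996 to 1.001 for these r). Stratifying takes power from 87.3 to 86.5% (r = 1.5), 87.1 to 86.2% (r = 2) and 87.5 to 85.1% (r = 3), a loss of 0.8, 0.9 and 2.4 points. A separate simulation with the 60%/25% mix, factor ratios of 2 to 3 and 5% a year of other censoring gave 83–84% falling to about 82%.

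**The case against.** The strongest reply is that the hazard-ratio part is not an error. The protocol names no model, so it neither commits to an unstratified estimate nor excludes a stratified one, and an analysis plan that is not shown may settle it. This stands: the protocol cannot be faulted for choosing an unstratified ratio, because it has not chosen.

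A reader might infer something stronger: that leaving out the factors pulls an inferior arm's ratio toward 1 and so makes the non-inferiority test unsafe. The direction is right for a within-stratum ratio, but the protocol does not define its limit that way. It takes the limit from whole-arm rates, where "a decrease in this rate to 70% would be the largest difference between treatments that can be judged as clinically acceptable". Against that limit the unstratified analysis keeps close to its nominal error. A within-stratum ratio of 1/0.63 gives a research-arm rate just above 70%, which is inside the limit. The gap is between two different quantities and does not show bias.

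It is also fair that the strength and prevalence of the factors are assumed, and that the TESS loss is on the conservative side. With SD 20 and 200 per arm, power for 10 points is already 99.9%, so lost precision would rarely change that conclusion.

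What remains is that the TESS and toxicity tests are named in unadjusted form, and that the margin is fixed without saying which ratio it governs.

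**Conclusion.** The point holds in modest form. The stated analyses do not use the factors that the randomisation uses. For TESS the effect is intervals that are too wide and a test at roughly 3 to 4% rather than 5%, without bias, if the factors explain 10 to 20% of the variance. For the hazard ratios the choice of strata matters only if the factors are prognostic and the true ratio differs from 1.

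Error above 5%, up to about 9%, needs three things together: 0.63 read as a within-stratum ratio, strong factors, and follow-up beyond two years. On the protocol's own whole-arm definition, error is about 4 to 5.4%, so the documents do not support calling the plan anti-conservative. No stated figure is wrong. All sizes rest on assumed prognostic strengths and prevalences, and any centre effect was left out.

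**What to change.** - **TESS:** analyse the two-year score and the area under the curve with a linear model that includes grade and clearance as recorded at randomisation, with centre as a random effect or pooled where sparse.
- **Local relapse, disease-free and overall survival:** estimate the hazard ratio from a Cox model stratified by grade and clearance, with the unstratified ratio as a sensitivity analysis.
- **Margin:** state that 0.63 was derived from whole-arm rates of 80% and 70%, so applying it to the stratified ratio is slightly stricter. Under the assumptions above, the same whole-arm limit corresponds to about 0.60 to 0.62 within strata.

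The text cost is a few sentences in section 6. The statistical cost is about 1 to 3 points of non-inferiority power when the arms are truly equal. TESS gains precision if the factors are prognostic.
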